#### 1) Findings on medical efficacy

Continuous oral administration of guanabenz acetate produced a dose-dependent decrease in metabolic parameters such as hepatic triglyceride (TG) content, hyperglycemia associated with insulin resistance, and blood levels of insulin and leptin in HFD-induced obese mice. However, the homeostasis model assessment beta (HOMA $\beta$ ) level, which indicates endogenous insulin secretory capacity, was not significantly affected by any dose of guanabenz acetate. The aforementioned low dose of guanabenz acetate for 14 days also significantly reduced hepatic TG content and blood glucose levels. The test results are presented in Fig. 1.

clinical trial protocol 番号 : YCU-21001

**Fig. 1.**

Weight gain from the start of administration (Fig. 1-1) and cumulative food intake (Fig. 1-2) ( $n = 7$  in each group). Liver TG content after 14 days administration (Fig. 1-3), insulin resistance (Fig. 1-4), blood glucose level (Fig. 1-5), insulin (Fig. 1-6) leptin (Fig. 1-6, 1-7) and HOMA  $\beta$  value (Fig. 1-8). Saline, G-Low, G-Med, and G-High indicate saline treatment and low-dose, medium-dose and high-dose treatment of guanabenz acetate, respectively. The data are shown as mean  $\pm$  standard error. \*  $P < 0.05$  and \*\*  $P < 0.01$  compared with the saline treatment group.

## 2) Findings relating to safety

All HFD-induced obese mice treated with all doses of guanabenz acetate remained healthy. Although weight loss was observed, the mice did not develop diarrhea during the experimental period. A daily change in BW and food intake after administration of various doses of guanabenz acetate in HFD-induced obese mice revealed a dose-dependent weight loss at day 14 of the oral administration of guanabenz acetate (Fig. 1-1). On the other hand, a decrease in cumulative food intake was observed only after high-dose administration, and no significant change was observed in low-dose and medium-dose mice (Fig. 1-2). Helz2 is negligibly expressed in the brain, including the hypothalamus, which is the feeding center, and its complete absence does not affect feeding. Therefore, the decrease in food intake observed after administration of a high-dose, which is three times the medium dose, may not be related to Helz2 function, while the anorexia effect on the brain derived from the  $\alpha 2$ -adrenergic receptor stimulating action of this drug may cause decreased feeding and weight loss.

## 1.4 Experience of clinical use

clinical trial protocol 番号 : YCU-21001

Many drugs with different mechanisms have been used in the treatment of hypertension. Guanabenz acetate (WYTENS® tablets) acts by a central mechanism called  $\alpha_2$  adrenergic receptor stimulating action involving the suppression of sympathetic nerve activity. However, this drug has been used for a long time since its launch in 1985 its use has been extremely limited. Use in patients with essential hypertension has been described, but there are no reports of experience in patients with non-alcoholic fatty liver disease, which is the subject of this clinical trial.

## 1.5 Summary of known and possible benefits and risks to the subject

### 1.5.1 Expected benefits of guanabenz acetate

In addition to improving fatty liver (NAFLD and NASH) associated with the improvement of insulin resistance induced by the action of guanabenz acetate on Helz2, improvement of diabetes, hyperlipidemia, and obesity is expected. In addition, improvement of hypertension based on the selective  $\alpha_2$ -adrenergic receptor stimulating action of guanabenz acetate is also expected.

### 1.5.2 Expected risks of guanabenz acetate

Guanabenz acetate suppresses peripheral sympathetic nerve activity by stimulating central sympathetic  $\alpha_2$  receptors. Reported adverse drug reactions include dry mouth (2.9%) as well as neuropsychiatric symptoms (2.8%), such as drowsiness and dizziness.

At present, it is unclear whether there is an adverse drug reaction derived from the effect of this drug on Helz2 or the resulting improvement in insulin resistance. As long as this drug is used within the approved dosage range, it is unlikely that an as-yet unknown adverse drug reaction will occur. Therefore, the main risk in this study is considered to be the known adverse drug reactions associated with the suppression of sympathetic nerve activity. The subjects of this study are hypertensive patients with NAFL. Their background is different from the approved target patients (essential hypertension). Therefore, the frequency and severity of adverse drug reactions may differ.

When administering guanabenz acetate, adverse drug reactions based on the suppression of sympathetic nerve activity as described above may occur and must be kept in mind. In addition, it is difficult to specifically assume an adverse drug reaction derived from the action on Helz2 or the improvement of insulin resistance induced by it. However, it is necessary to carefully observe changes in metabolic parameters such as BW, blood glucose, and lipids, which are thought to have an effect, and to clarify the clinical profile of this drug.

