#### 8.5.3 Pre-administration observation, examination, survey items (V2)

- Selection criteria
- Physical examination
- Vital signs
- Subjective and objective symptoms
- Pregnancy test
- Hematology / coagulation \*, urinalysis \*
- Biochemical test 1 \*
- Biochemical test 2 \*
- Others
- Genetic testing
- Concomitant drug

\*If there is data within 4 weeks, it can be substituted.

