## 9 Observation, inspection, evaluation items, and timing

### 9.1 Observation, inspection, and evaluation schedule list

The principal investigator or sub-investigator conducts observations, inspections, surveys, etc. according to the table below. If a blood sampling test is to be performed at the time of the subject's visit, the subject should fast for 8 hours before the blood is collected.

Table 9.1-1 Observation, examination, and evaluation schedule

		8-week	16-week						4-week
Screening		Group A: WY-8678 4 mg/day: one tablet per session, twice per day						Follow-up	
		Group B: WY-8678 8 mg/day: 2 tablets per session, twice per day							
Week	Consent acquisition	Screening	Treatment period						Follow-up
		V1	V2	V3	V4	V5	V6	V7/EOT	V8
		Within 8 weeks prior to registration	Prior to start of administration	2 weeks	4 weeks	8 weeks	12 weeks	16 weeks	4 weeks after end of administration
Tolerable range		-8 weeks	-	±3 days	±7 days	±7 days	±7 days	±7 days	±7 days
Consent acquisition	○								
Selection criteria		○	○						
Subject background		○							
Serological test a		○							
Chest X-ray		○							
Electro-cardiogram		○							
Physical examination b		○	○					○	
Vital signs c		○	○	○	○	○	○	○	○
Subjective and objective symptoms			○	○	○	○	○	○	○
Pregnancy test d			○					○	
MRI e		○						○	
Liver biopsy		△							
Randomization			○						
Hematology test / urine test f		○	○ i					○	○
Endocrinological examination		○							
Biochemical test 1		○	○ i		○	○	○	○	○
Biochemical test 2 g		○	○ i					○	
Other h			○					○	
Somatic cell genetic test			●						
Providing drugs			○		○	○	○		
Checking the medication status				○	○	○	○	○	
Survey of combination drugs		○	○	○	○	○	○	○	
Investigation of adverse events				○	○	○	○	○	○

○: Implemented

△: Information is collected for cases with liver biopsy results (within 32 weeks before screening).

●: Genetic testing is an essential test.

a: Contains HBs antigen, HCV antibody, and HCV-RNA.

b: Includes height (V1 only) and weight. BMI (V1) is calculated based on height and weight.

c: Vital signs include blood pressure, pulse rate, and axillary body temperature.

d: For women of childbearing potential, a urine pregnancy test will be performed on V2 and V7.

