e: Use MRI to measure MR elastography (MRE) and liver fat (PDFF). Patients terminating before V7 (week 16) should undergo MRI at the end of treatment if they have completed at least 4 weeks of treatment.

clinical trial protocol 番号 : YCU-21001

f-h: Refer to Table 9.1-2 Clinical laboratory items.  
i: If there is data within 4 weeks, it can be substituted.

Table 9.1-2 Clinical laboratory items

Biochemical test 1 (on an empty stomach) (Screening, every visit, follow-up, termination)	Biochemical test 2 (on an empty stomach) (At the time of screening, V2, V7, termination)	Others (V2, V7/at termination)
Albumin (Alb) ALT Alkaline phosphatase (ALP) Amylase AST Blood urea nitrogen (BUN) Chlorine (Cl) Creatinine (Cre) Estimated glomerular filtration rate (eGFR)  (during screening) $\gamma$ -GTP Lactate dehydrogenase (LDH) Potassium (K) Sodium (Na) Calcium (Ca) Total bilirubin (T-Bil) Total protein (TP) Uric acid	HDL-C LDL-C Non-HDL-C  TC TG  Glucose HbA1c Insulin HOMA-IR 	[Inflammation] High-sensitivity C-reactive protein (CRP) Ferritin TNF- $\alpha$ Interleukin-6 CK18 / M30 Endotoxin LBP Endotoxin activity [Endocrine] C-peptide Total GLP-1 / Active GLP1 Leptin Adiponectin [Fibrosis] hyaluronic acid PIIP TIMP-1 M2BPGi Type IV Collagen 7s ELF score3 Fibrosis-4 (FIB-4)  [Fat] Chylomicron cholesterol Chylomicron triglyceride Lipoprotein cholesterol LDL triglyceride VLDL cholesterol VLDL triglyceride Free cholesterol (F-cho) Apolipoprotein A1 Apolipoprotein B Adipsin Free fatty acid (FFA) [Others] TMAO
Hematological examination / coagulation (During screening, V2, V7, follow-up, termination)	Urinalysis (Screening, V2, V7, termination, follow-up)	
Hematocrit (Ht) Hemoglobin (Hb) Platelet count Number of red blood cells White blood cell count and white blood cell fraction (neutrophils, eosinophils, basophils, lymphocytes, monocytes) International Normalized Ratio (INR)	Latent blood Urine sugar pH Urine protein Specific gravity Urobilinogen  Pregnancy test  (At V2, V7, at termination)	
Somatic cell genetic test (V2)	Endocrinological examination (at the time of screening)	Serological test (at the time of screening)
PNPLA3 TM6SF2	Free thyroxine (FT4) Free triiodothyronine (FT3) Thyroid stimulating hormone	HBs antigen HCV antibody 

 Postmenopausal is defined as a condition without medical causes and no menstruation for more than 12 months.

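### Body weight and blood glucose are not scheduled between the first dose and week 16, although the protocol asks for both to be watched carefully

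*Protocol*

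**What the plan says.** The section on expected risks (Protocol 1.5.2) states that "it is necessary to carefully observe changes in metabolic parameters such as BW, blood glucose, and lipids". The stated aim is a clearer picture of how the drug behaves clinically. No frequency is given.

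The schedule (Table 9.1-1, repeated in the Summary) fixes when these are measured:

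- **Weight** belongs to the physical examination ("b: Includes height (V1 only) and weight"), which is marked at V1, V2 and V7/EOT. Vital signs are taken at every visit but consist of blood pressure, pulse and temperature.
- **Blood glucose** belongs to the second biochemical panel, headed in Table 9.1-2 "Biochemical test 2 (on an empty stomach) (At the time of screening, V2, V7, termination". HbA1c, insulin and the standard lipids are in the same panel.
- **V4, V5 and V6** (section 8.5.5) have the first biochemical panel, which contains no glucose. V3 (section 8.5.4) has no laboratory test.
- **V8** (section 8.5.7) has urinalysis, which includes urine sugar, but neither weight nor blood glucose.

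Section 8.1.3 places the first dose after dinner on the day of V2, so the V2 values are pre-dose. Section 8.3.2 allows sulfonylureas and other listed oral diabetes drugs at a constant dose until study drug ends, with gradual reduction permitted if symptoms worsen. Section 1.5.1 lists improvement of diabetes and obesity among the expected benefits.

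**The concern.** The protocol names weight and glucose as quantities to watch because their response to this drug is not known in these patients, then leaves the whole treatment period up to its last visit without a scheduled value of either. Its own mouse data suggest that effects could come early: "The aforementioned low dose of guanabenz acetate for 14 days also significantly reduced hepatic TG content and blood glucose levels", and daily weights "revealed a dose-dependent weight loss at day 14 of the oral administration of guanabenz acetate". The human time course is unknown, which is itself a reason to look before week 16.

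The subjects for whom this matters most are those with type 2 diabetes on a sulfonylurea. Entry is allowed with HbA1c up to 9.5%, provided that the diabetes is not uncontrolled (section 4.3). If glycaemia improves as section 1.5.1 expects, a fixed sulfonylurea dose may become too high. Section 8.3.2 allows a reduction, but the trigger is symptoms and no glucose value is scheduled to inform it. Section 1.5.2 lists drowsiness and dizziness as known reactions to guanabenz, so symptoms alone may not separate a drug effect from low glucose; that last step is an inference and not a statement of the protocol.

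**Working it through.** No stated figure has to be reproduced. The check is a count of scheduled measurements for a subject who completes treatment, from Tables 9.1-1 and 9.1-2 and sections 8.5.2 to 8.5.7.

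| Visit | Week (window) | Weight | Blood glucose |
|---|---|---|---|
| V1 | screening | yes | yes |
| V2 | pre-dose | yes | yes |
| V3 | 2 (±3 days) | no | no |
| V4 | 4 (±7 days) | no | no |
| V5 | 8 (±7 days) | no | no |
| V6 | 12 (±7 days) | no | no |
| V7/EOT | 16 (±7 days) | yes | yes |
| V8 | 4 weeks after the last dose (±7 days) | no | no (urine sugar only) |

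**Present schedule**

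- On-treatment visits are V3 to V7, which is 5. Weight and glucose are measured at 1 of them (V7).
- Time from first dose to first on-treatment value: 16 ± 1 = 15 to 17 weeks.
- Scheduled values after treatment: 0.

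**With weight and fasting glucose added at V4, V5 and V6**

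- First on-treatment value: 4 ± 1 = week 3 to 5.
- Longest gap between later on-treatment values: V4 to V5 is at most (8 + 1) − (4 − 1) = 6 weeks. V5 to V6 and V6 to V7 have the same spacing and windows, so 6 weeks again.
- On-treatment values per completer rise from 1 to 4 (V4, V5, V6, V7).

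**Feasibility.** The first biochemical panel is already drawn fasting at V4, V5 and V6, and section 9.1 requires for any blood test that "the subject should fast for 8 hours before the blood is collected". A glucose added there is a fasting glucose without any further preparation by the subject.

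**Burden.** 28 subjects × 3 visits = 84 weights and 84 glucose assays. With V8 as well, 28 × 4 = 112 of each.

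**The case against.** The strongest reply is that nothing here is wrong. Section 1.5.2 sets no frequency, and the protocol does observe weight, glucose and lipids before and after treatment, with weight, lipids and HOMA-IR as secondary endpoints at week 16. This stands: the schedule does not contradict section 1.5.2.

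A reader might infer that a fall in glucose or weight starting during treatment goes unseen. The documents do not support that. A change that persists is seen at V7, where weight, fasting glucose and HbA1c are all measured, and a subject who stops early has the same tests at termination. Only a change that is early or transient and without symptoms escapes.

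A reader might also infer a hypoglycaemia hazard for sulfonylurea users. The protocol names none. Section 1.3 describes reduced hyperglycaemia in obese mice, no significant effect on HOMA-beta, and animals that stayed healthy. Both doses are within the approved range. Uncontrolled type 2 diabetes and insulin use are excluded. Symptoms and adverse events are reviewed at every visit from V3, subjects keep a diary, section 11.1 requires continuing contact with the subject, section 12.1 lets the investigator stop treatment, and unscheduled tests are not forbidden. These safeguards cover the symptomatic case well. They do not supply a value for a symptom-free change, or a scheduled one when a dose reduction is being considered.

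A longer gap can be constructed, because section 8.5.3 says of the V2 laboratory data: "If there is data within 4 weeks, it can be substituted". That gives 17 + 4 = 21 weeks between glucose values, but up to 4 of those weeks precede the first dose. The time on drug without a value is at most 17 weeks.

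Finally, four-weekly fasting glucose shows a trend and will not catch every intermittent low. That is also true, and it limits what the addition can achieve.

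**Conclusion.** The point holds as a cheap safety improvement to consider. For a completer, weight and blood glucose are each measured at 1 of 5 on-treatment visits, 15 to 17 weeks after the first dose, in a trial whose risk section asks for careful observation of both. What is lost is sight of an early or transient symptom-free change, and any scheduled glucose to guide a sulfonylurea reduction during treatment.

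The count rests on the schedule as written and needs no assumption. The clinical weight of the gap depends on two things that the protocol does not give: the time course of any metabolic effect in humans, and the number of subjects on a sulfonylurea, which could be zero. It is therefore a precaution. The primary endpoint and the baseline-to-week-16 comparisons are not affected.

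**What to change.** Add body weight and fasting glucose at V4, V5 and V6, taken with the existing fasting draw for the first biochemical panel. This changes section 8.5.5, Tables 9.1-1 and 9.1-2, and the schedule in the Summary.

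V8 is optional and would also change section 8.5.7. Concomitant drugs are no longer restricted after study drug ends (section 8.3.2), so a V8 value would not cleanly show the course after stopping. Standard lipids have the same gap and could be added at the same draws, but are not needed for the safety purpose.

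The cost is a schedule amendment and at most 84 extra weights and 84 extra glucose assays (112 of each with V8), possibly with an extra tube, since the protocol does not describe tubes or volumes for these panels. If assay cost matters, glucose can be limited to the s subjects on a diabetes drug, which makes it 3s assays over V4 to V6. No new visit or fast is needed.

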## 2 Compliance with laws and regulations regarding GCP and this clinical trial

This clinical trial is conducted in compliance with the Declaration of Helsinki, clinical trial protocol, criteria specified in "Act on Securing Quality, Efficacy and Safety of Products Including Pharmaceuticals and Medical Devices" Article 14-3 and Article 80-2, and "Guideline for Good Clinical Practice" (GCP). The implementation of the trial will comply with the ethical principles of the Declaration of Helsinki and maximize the human rights, welfare, and safety of the subjects.

## 3 Purpose of clinical trial

### 3.1 Purpose

We will investigate the efficacy and safety of 4 mg/day and 8 mg/day of WY-8678 (guanabenz acetate) in NAFLD/NASH patients with hypertension.

### 3.2 Phase of development

Phase IIa

## 4 Subjects

clinical trial protocol 番号 : YCU-21001

#### 4.1 Subject disease NAFLD/NASH

##### 【Setting basis】

NAFLD in Japan affects 20 to 40% of adults. As a phenotype of metabolic syndrome in the liver, NAFLD is often associated with obesity, diabetes, dyslipidemia, hypertension, and other conditions. When it progresses to NASH, the risk of developing liver cirrhosis and liver cancer increases, and the risk of developing cardiovascular events is high. Therefore, preventing the progression of the condition by intervention is important. Rapid improvement of the pathological condition is required in NASH. If treatment with drugs becomes possible, it will lead to a significant decrease in patients with liver cirrhosis, liver cancer, and patients with cardiovascular events. Since the investigational drug being evaluated is a therapeutic drug for hypertension and the frequency of NAFLD complications in hypertensive patients is high, NAFLD patients including NASH with hypertension should be set as a target group for which the medical efficacy for the pathological condition can be properly judged. This clinical trial is a clinical phase IIa study aimed at confirming the proof of-of-concept (POC) of guanabenz acetate therapy. We plan to examine the target and staging in the next phase.

#### 4.2 Selection criteria

Subjects include patients who meet the following criteria at the time of screening.

1. Patients who have been fully informed about this study and have provided their written consent.
2. Patients aged  $\geq 20$  years and  $\leq 75$  years at the time of consent.
3. Patients diagnosed with essential hypertension and whose blood pressure at the time of screening is systolic blood pressure  $\geq 130$  mmHg and/or diastolic blood pressure  $\geq 85$  mmHg (according to the diagnostic criteria for metabolic syndrome).
4. Patients diagnosed with NAFLD/NASH who meet the following criteria (1) or (2):
  - (1) Patients diagnosed with NAFLD who meet the following three items
    - ① Diagnostic imaging or histological detection of fatty liver,
    - ② Alcohol intake  $< 30$  g/day for men and  $< 20$  g/day for women for at least 12 consecutive weeks in the year before screening,
    - ③ Absence of other factors that cause fattening or chronic liver disease.
  - (2) Patients with a definitive diagnosis of NASH by biopsy within 32 weeks before screening  
\* The definitive diagnostic criteria for NASH are defined as a fibrosis stage in liver biopsy in the evaluation using the "NASH Clinical Research Network (CRN) criteria" by an F1-F3 pathologist and a NAFLD activity score (NAS)  $\geq 4$  points (each item has one or more points):
    - ① Fattening (0-3 points)
    - ② Balloon-like swelling (0 to 2 points)
    - ③ Inflammation in the lobules (0-3 points)
5. Patients with MRI-proton density fat fraction (PDFF) liver fat mass  $\geq 8\%$  at screening.
6. Patients with magnetic resonance elastography (MRE) value  $\leq 3.6$  kPa at screening.
7. Patients with BMI  $\geq 25$  kg/m^2 or more at the time of screening.
8. Patients receiving diet or exercise therapy 12 weeks before screening, with no improvement.
9. Patients who are willing to maintain a stable diet and physical activity during the clinical trial.

##### 【Setting basis】

1. Ethical considerations

clinical trial protocol 番号 : YCU-21001

2. When voluntarily participating in a clinical trial, the person must be at least 20 years old for whom consent is legally established individually. In addition, considering the predominant age and safety of NAFLD/NASH, the upper limit is 75 years.
3. The disease is the target of the investigational drug. Blood pressure values set as the diagnostic criteria for metabolic syndrome associated with NAFLD are those formulated in 2005 by eight societies: Japan Atherosclerosis Society, Japan Diabetes Society, Japan Society for the Study of Obesity, Japan Society of Hypertension, Japanese Circulation Society, Japanese Society for Pediatric Nephrology, Japanese Society on Thrombosis and Hemostasis, and Japanese Society of Internal Medicine.
4. As a diagnostic criterion for NASH and considering the high risk of developing fibrosis, a NAS score  $\geq 4$ , which has been widely defined in clinical trials internationally, was set. The diagnostic criteria for NAFLD were set in accordance with the 2014 NAFLD/NASH clinical practice guidelines.
- 5-7. Since the purpose of the clinical trial is to evaluate the effect of this investigational drug, it was set to set a certain standard for the target subjects in consideration of the effect on the efficacy evaluation.
- 8.9. The effects of changes in the dietary environment and exercise load on NAFLD pathology were minimized as much as possible.

#### 4.3 Exclusion criteria

Patients who meet the following criteria at the time of screening are excluded:

1. Pregnant, lactating, potentially pregnant women, or patients who do not agree to contraception during the trial period.
2. Patients who have taken guanabenz acetate within 16 weeks prior to screening or who have participated in other clinical studies. Observational studies are excluded.
3. Patients with drug allergies to guanabenz acetate.
4. Patients with liver failure or cirrhosis.
5. Patients with the following laboratory test values:
  - (1) ALT  $> 430$  IU/L (males) or  $> 240$  IU/L (females); or AST  $> 300$  IU/L
  - (2) PT-INR  $\geq 1.5$  (excluding anticoagulant therapy)
  - (3) Total bilirubin value  $> 2.0$  mg/dL (excluding definitive diagnosis of Gilbert syndrome)
  - (4) Platelet count  $< 80,000/\mu\text{L}$
  - (5) eGFR  $< 45$  (calculated by body surface area correction: standardized eGFR)
6. Patients with a history of acute or chronic liver disease other than NAFLD/NASH and complications:
  - (1) Patients suffering from hepatitis B (HBs antigen positive at the time of screening) or hepatitis C (HCV antibody positive at the time of screening).  
HCV antibody-positive patients who are negative for HCV-RNA can be registered if they are confirmed to be negative for at least one year before screening.
  - (2) Patients with autoimmune hepatitis.
  - (3) Patients with primary biliary cholangitis, primary sclerosing cholangitis, Wilson's disease,  $\alpha$ 1-antitrypsin deficiency, hemochromatosis or iron overload, drug-induced or alcoholic liver disease, or a history of known biliary atresia.
  - (4) Patients with suspicion or definitive diagnosis of hepatocellular carcinoma.
7. Patients with a history of HIV infection.
8. Patients with findings of portal hypertension (complications include ascites, hepatic encephalopathy, varicose veins, and splenomegaly).
9. Patients with a history of use of NAFLD-related drugs (amiodarone, methotrexate, systemic glucocorticoids, tetracycline, and tamoxifen, or higher doses of estrogen, anabolic steroids, or valproic acid than used for hormone replacement) or other hepatotoxins for at least 4 weeks prior to screening.
10. Patients who have used the following drugs:

clinical trial protocol 番号 : YCU-21001

- (1) Insulin, glucagon-like peptide-1 (GLP-1) receptor agonists, sodium-glucose transport protein 2 (SGLT2) inhibitors, or thiazolidine 12 weeks before screening
  - (2) Ursodeoxycholic acid or vitamin E 12 weeks before screening
  - (3) Altered doses of dyslipidemia drugs or antihypertensive drugs 12 weeks before screening
  - (4) Altered dose of oral diabetes treatment drug (DPP-4 inhibitor, SU preparation,  $\alpha$ -glucosidase inhibitor, metformin) 12 weeks before screening
  - (5) Those with a significant effect on body weight (including over-the-counter drugs for weight loss) 12 weeks before screening
  - (6) Central nervous system depressants (barbital, sodium thiopental, morphine hydrochloride hydrate, brotizolam, diazepam, etc.)
11. Patients with 10% weight change 24 weeks before screening.
  12. Patients scheduled to undergo surgery after obesity surgery (such as gastroplasty and Roux-en-Y gastric bypass surgery) or during the trial period.
  13. Patients with a history of type 1 diabetes.
  14. Patients with HbA1c > 9.5% at screening or with uncontrolled type 2 diabetes.
  15. Patients with hyperthyroidism or hypothyroidism, or with screening results showing thyroid dysfunction. For hypothyroidism, registration is possible if thyroid replacement therapy is received 12 weeks before screening and the test values are stable.
  16. Patients with a history of New York Heart Association (NYHA) functional classification class III or IV heart failure due to factors other than hypertension.
  17. Patients with a history of myocardial infarction, unstable angina, percutaneous coronary intervention, coronary artery bypass grafting, or stroke or major surgery 24 weeks before screening.
  18. Patients with a history of substance abuse.
  19. Patients with malignant tumors.  
Patients who have undergone radical surgery, patients who have completed chemotherapy/radiation therapy and patients who are undergoing hormone therapy can be registered.
  20. Patients with known intolerance to MRI or patients who are contraindicated for MRI examination.
  21. Other patients who the principal or sub-investigator deems inappropriate for conducting this clinical trial.

